14.3.3 Upper to Lower Body Segment Ratio

The upper to lower body segment ratio will be calculated at each visit as follows:

$$\text{Upper to Lower Body Segment Ratio} = \frac{\text{Derived Sitting height(cm)}}{\text{Derived Standing height(cm)} - \text{derived Sitting height(cm)}}$$

The ratio of derived sitting height and derived standing height will also be calculated.

The upper to lower body segment ratio, the sitting to standing height ratio, and their change from baseline will be summarized and presented separately by cohort by treatment group using the format as specified in [Table 5.1](#), [Table 5.2](#), and [Table 5.3](#) for Cohorts 1, 2, and 3, respectively.

Upper to lower body segment ratio will be analyzed using the same methods and estimand formulation as the primary efficacy endpoint analysis and sensitivity analyses, an analysis of change from baseline in the upper to lower body segment ratio at Week 52 will be performed using an ANCOVA model that includes the fixed-effects of treatment (active arm vs. placebo arm) and baseline covariates, where baseline covariates include randomization age stratum, age at baseline, sex, baseline AGV, and baseline upper to lower body segment ratio.

Upper to lower body segment ratio and sitting to standing height ratio derived for all visits will be included in data listings including data from 111-901 and 111-206.

A line plot of individual upper to lower body segment ratio will be presented at baseline and Week 52 for each subject by cohort by stratified age stratum. A line plot of the mean (+/-SD) upper to lower body segment ratio will be presented by cohort at 6 Months Prior (3-month prior for Subjects in Cohort 3), Baseline, Week 26 and Week 52.

14.3.4 Body Proportion Ratios

Body proportion ratios include:

- Upper Arm Length to Lower Arm (Forearm) Length Ratio
- Upper Leg Length (Thigh) to Knee to Heel Length Ratio

- Upper Leg Length (Thigh) to Tibial Length Ratio
- Arm Span to Standing Height Ratio

The absolute values and its change from baseline will be summarized and presented separately by cohort by treatment group using the format as specified in [Table 5.1](#), [Table 5.2](#), and [Table 5.3](#) for Cohorts 1, 2, and 3, respectively.

All assessments will be listed.

14.3.5 Other Growth Measures

Other growth measures include:

- Sitting Height (cm)/Crown to Rump (cm)
- Upper Leg Length (Thigh) (cm)
- Lower Leg Length: Knee to Foot (cm)
- Lower Leg Length: Tibia Length (cm)
- Head Circumference (cm)
- Upper Arm Length (cm)
- Lower Arm (Forearm) Length (cm)
- Arm Span (cm)

In addition, derived standing height and derived sitting height will be calculated as specified in [Section 14.1](#), and a measure of lower body length will be calculated as follows:

- Lower Body Length (cm) = Derived Standing height – Derived Sitting height

Baseline growth measures are those assessed on Day 1, regardless of timing relative to dosing. All summaries and analyses will be based on the FAS.

For each of the above growth measures (including lower body length), the absolute values and its change from baseline will be summarized and presented by cohort by treatment group using the format as specified in [Table 5.1](#), [Table 5.2](#), and [Table 5.3](#) for Cohorts 1, 2, and 3, respectively.

All assessments will be listed by subject and visit.

14.4 Health-Related Quality of Life

The Health-Related Quality of Life (HRQoL) questionnaires and functional independence questionnaires are captured at Baseline, Week 26, Week 52. All summaries will be generated on the FAS.

Each table will include summaries of the absolute measures at each of these time points and change from baseline at every 26 weeks. The tables will be summarized separately by cohort by treatment group using the format as specified in [Table 5.1](#), [Table 5.2](#), and [Table 5.3](#) for Cohorts 1, 2, and 3, respectively.

The statistical summaries will include the number of subjects with assessable data, mean, SD, median, 25th and 75th percentile, minimum and maximum. Subjects will not be included in a summary table if there is no baseline assessment available.

Separate summary tables will be provided for the total summary scores and the individual domains (scales). Individual questions (items) are not included in the summary tables.

Age-defined versions within the same questionnaire will be summarized together. If subjects progress during the course of the study from one age-defined questionnaire to the next age-defined questionnaire the results will be summarized together and the baseline assessment from the child's first questionnaire is referred to when summarizing change from baseline.

If a questionnaire for the wrong age group was filled, outcomes will not be included in the summary table but will be included in the listings.

Self-reports and parent-reports will be summarized separately but together in the bat charts.

All subject data listings will include total scores, and domain (scale) scores.

14.4.1 Bayley-III

The Bayley-III is a performance-based outcome assessment for use in children from 1 to 42 months.

Scales include Cognitive scale, Language (Receptive Communication and Expressive Communication subscales) scale, and Motor (Gross and Fine Motor subscales) scales.

In addition to its use for subjects ranging from 1 to 42 months old, the Bayley-III assessment will be administered to those entering the study between 42 and 60 months old and for the remainder of the duration of this study, as this assessment can capture ongoing developmental issues associated with ACH. Bayley-III is waived for subjects < 1 month old.

Scales/Subscales:

- Cognitive
- Language
 - Receptive Communication
 - Expressive Communication

- Motor
 - Fine Motor
 - Gross Motor

Each (sub)scale yields a total raw score which is then standardized according to the subject's chronological age (scaled scores).

Scoring

Number of items depends on which set is given in each domain. The number of questions administered depends in part on the child's age and on their developmental level.

The total raw scores for the Cognitive Scale and the Receptive Communication, Expressive Communication, Fine Motor, and Gross Motor subscale are the sums of the number of points earned for a (sub)scale.

The raw scores cannot be accurately compared to each other as each subscale has a different number of items resulting in a different range of possible scores. Therefore, the comparisons are best based on derived scores: age-based scaled scores or composite scores⁸.

Scaled scores represent a child's performance on a (sub)scale relative to the same age peers. They are derived from the total raw scores on each of the subscale and are scaled to a metric with a range of 1 to 19, a mean of 10 and a SD of 3.

Composite scores are scaled to a metric with a mean of 100 and a SD of 15, and range from 40–160.

For the Language and Motor Scale, composite scores are derived from the sums of age-corrected scaled scores. For each composite, the distribution of the sum of scaled scores is used to derive corresponding percentiles which are converted to composite scores with a mean of 100 and a standard deviation of 15.

For the Cognitive subdomain the scaled score to composite equivalent is a linear conversion from one scale (mean=10, SD=3) to another (mean=100, SD=15).

For the scaled scores and composite scores, the absolute values will be summarized separately by cohort by treatment group using the format as specified in [Table 5.1](#), [Table 5.2](#), and [Table 5.3](#) for Cohorts 1, 2, and 3, respectively.

The 3 composite scores (Cognitive, Language and Motor) will be displayed by cohort and treatment group in a bar chart.

14.4.2 Infant and Toddler Quality of Life Questionnaire ([itqol-97, 2013](#)) (ITQOL)

The Infant Toddler Quality of Life questionnaire (ITQOL) is an observer-reported outcome tool developed for use in children from 2 months to 5 years old that attempts to capture physical, mental and social well-being. The ITQOL adopts the World Health Organization's definition of health as a state of complete physical, mental and social well-being, and not merely the absence of disease. The ITQOL also assesses the quality of the parents/guardians' life. The 97-item full-length version (ITQOL) will be used for this study. ITQOL is waived for subjects < 2 months old.

Domains

The following domains are part of the ITQoL:

- Overall Health (1item)
- Physical abilities (10 items)
- Growth and development (10 items)
- Pain (3 items)
- Temperament and mood (18 items)
- Behavior (12 items)
- Global behavior (1 items)
- Getting on with others (15 items)
- Global health perceptions (11 items)
- Change in health (1 item)
- Parental impact emotional (7 items)
- Parental impact time (7 items)
- Family cohesion (1 item)

For the ITQOL, the exact number of items that can be missing differs depending on which section is being scored, though the general rule is that a section can be scored if at least half the responses in that section were completed.

Summary scores for the 13 domains (overall score) will be summarized separately by cohort by treatment group using the format as specified in [Table 5.1](#), [Table 5.2](#), and [Table 5.3](#) for Cohorts 1, 2, and 3, respectively.

The summary scores for Overall Health, Physical Abilities and Growth and Development will be displayed separately for the sentinel and randomized subjects by cohort and treatment group in a bar chart.

14.4.3 Function Independence Measure (WeeFIM) (Wee-FIM II Version 6.4)

The WeeFIM (Functional Independence Measure for children) instrument is a functional independence assessment tool that measures functional performance across three domains (self-care, mobility and cognition) from the caregiver's perspective.

Performance of a child on each of the individual items within the WeeFIM is assigned to one of seven levels on an ordinal scale that represent the function from complete and modified independence (levels 7 and 6) without a helping person to modified and complete dependence (levels 5 to 1) with a helping person.

If individual items (questions) within a domain are missing, the item result is imputed to 1, per guidance in The WeeFIM Clinical Guide v 6.49.

If all items for a domain score are missing the domain score is considered missing.

If a domain score is missing, the Total score is missing.

For each of the following domains and the total score, the absolute values at each scheduled visit, and change from baseline at each scheduled visit, will be summarized separately by cohort by treatment group using the format as specified in [Table 5.1](#), [Table 5.2](#), and [Table 5.3](#) for Cohorts 1, 2, and 3, respectively:

- Self-care Score (min score=8, max score=56)
- Mobility Score (min score=5, max score =35)
- Cognition Score (min score=5, max score=35)
- Total WeeFIM rating (min=18, max=126)

Domain and total scores will be listed by cohort, sentinel/randomized subjects, treatment group, and subject number.

Note: Although each domain will be summarized so that all aspects of this validated scale are reported, the cognition aspect of the WeeFIM (cognition subtotal score) is considered not to be of concern for subjects with achondroplasia.

The three domains and Total WeeFIM score will also be displayed by visit in a bar chart and presented separately for the sentinel and randomized subjects by cohort and treatment group.

14.5 Sleep Study Scores

A sleep study will be performed in a limited number of qualified sleep centers. A sleep-testing device will be used to assess the presence and severity of sleep-disordered breathing by measurement of blood oxygen saturation, pulse rate, and airflow during overnight monitoring. Assessment of episodes of sleep apnea will include, but may not be limited to, the number of episodes of apnea and hypopnea per hour (Apnea/Hypopnea Index). Sleep study data is collected at Screening, Week 52, and early termination visit.

Following episodes of sleep apnea variables will be summarized separately by cohort by treatment group using the format as specified in [Table 5.1](#), [Table 5.2](#), and [Table 5.3](#) for Cohorts 1, 2, and 3, respectively.

- Number of episodes of apnea per hour (Apnea Index).
- Number of episodes of hypopnea per hour (Hypopnea Index).
- Number of episodes of obstructive apnea hypopneas per hour (Apnea Hypopnea Index)
- Number of episodes of obstructive apneas per hour (Obstructive Apnea Index)
- Number of episodes of central apneas per hour (Central Apneas Index)
- Number of desaturations per hour $\geq 3\%$

Listing of the above episode of sleep apnea variables will be provided.

15 SAFETY EVALUATIONS

The safety population will be used for all safety summaries.

Summary tables assessing safety parameters at planned visits over time will include all safety events up to 30 days following treatment discontinuation. These summary tables will be presented separately by cohort and overall by treatment group using format as specified in [Table 5.4](#). Listings will include all reported data.

Safety will be assessed by examining the incidence, frequency, severity (determined using the CTCAE version 4.03), and relationship to study treatment of all TEAEs reported during the study period. In addition, changes from baseline in clinical laboratory results and vital signs will be assessed.

15.1 Adverse Events

Adverse events (AEs) will be coded in accordance with MedDRA Version 24.1 and performed prior to DBL. Coding of the severity of AEs is performed by the investigators using national cancer institute (NCI) CTCAE version 4.03, where events are coded from CTCAE Grade 1 to Grade 5.

Only TEAEs defined as any adverse event that newly appeared, increased in frequency, or worsened in severity following initiation of study treatment administration are reported by the investigators and consequently are included in the summary tables.

In the event that the start date of an AE is incomplete or missing, conservative imputation rules are applied so that where there is uncertainty, the event is considered treatment emergent. Similarly, the AE end dates are imputed in a conservative manner to a maximum length.

15.1.1 Treatment-Emergent Adverse Events

Treatment-emergent adverse events (TEAEs) will be summarized separately by cohort and overall by treatment group using format as specified in [Table 5.4](#). In summaries by SOC and/or PT, subjects with more than one AE of the same SOC or PT will be counted once within that SOC/PT. For those AEs that occurred more than once during the study, AEs by severity will be summarized by the maximum CTCAE grade and by all CTCAE grades. The tables are ordered by the descending frequency of SOC or PT of overall in the table.

The following summary tables will be provided:

- Overview of the incidence of TEAEs
- Overview of exposure-adjusted event rates of TEAEs
- Incidence and exposure-adjusted event rates of TEAEs by SOC, PT, and CTCAE grade
- Incidence of TEAEs by SOC, PT and highest CTCAE grade
- Incidence of and exposure-adjusted event rates TEAEs by PT
- Incidence of TEAEs by SOC
- Incidence of and exposure-adjusted event rates treatment related TEAEs by SOC, PT and CTCAE grade
- Incidence of and exposure-adjusted event rates TEAEs with CTCAE Grade ≥ 3 by SOC, PT and CTCAE grade
- Incidence of serious adverse events (SAEs) by SOC and PT
- Incidence of non-serious adverse events by SOC and PT
- Incidence of TEAEs leading to study or study treatment discontinuation by PT
- Incidence of TEAEs leading to study treatment interruption by PT
- Incidence of TEAEs leading to study treatment dose reduction by PT
- Incidence of achondroplasia related TEAEs by SOC and PT*

* Achondroplasia-related TEAEs will be identified using the PTs identified for achondroplasia-related medical history (see Section 10). In addition, all AEs will be reviewed prior to DBL and the list updated as required.

For exposure-adjusted event rates of TEAEs, exposure will be derived to up to the last dose reported in the study database.

Listings:

In addition to the above tables, the following listings will be provided and ordered by subject and AE start date:

- All TEAEs
- TEAEs with CTCAE Grade ≥ 3
- Achondroplasia-related TEAEs
- SAEs
- Deaths

- TEAEs leading to study or study treatment discontinuation
- TEAEs leading to study treatment interruption or dose reduction
- TEAEs of confirmed/suspected COVID-19
- TEAEs occurring within 14 days following COVID-19 Vaccine

15.1.2 Events of Interest

Events of interest (EOI) will be summarized by PT separately by cohort and overall by treatment group using format as specified in [Table 5.4](#). For those AEs that occurred more than once during the study, the maximum severity will be used to summarize the AEs by severity.

The following are identified as events of interest:

Injection site reactions (ISR)

- TEAEs with a MedDRA High Level Term (HLT) of “Injection site reaction”.

Hypotension

- TEAEs with PT: Blood pressure ambulatory decreased, Blood pressure decreased, Blood pressure diastolic decreased, Blood pressure orthostatic decreased, Blood pressure systolic decreased, Blood pressure systolic inspiratory decreased, Diastolic hypotension, Hypotension, Orthostatic hypotension.

Heart rate change

- TEAEs with a PT: Atrial tachycardia, Postural orthostatic tachycardia syndrome, Rebound tachycardia, Sinus tachycardia, Supraventricular tachycardia, Tachycardia, Tachycardia paroxysmal, Ventricular tachycardia, Bradycardia.

Hypersensitivity SMQ

- TEAEs with a PT included in the MedDRA hypersensitivity SMQ

Algorithmic Anaphylaxis SMQ (with sponsor-defined time restrictions)

- TEAEs with a PT included in the MedDRA anaphylactic reaction SMQ, with an additional time restriction: a narrow scope PT within 48 hours of a dose, or two broad scope PTs from different classes where both PTs are within 48 hours of the same dose.

Fractures

- TEAEs with a PT containing the term “fracture” and also PTs of Bone fragmentation, Bone fissure, Scapulothoracic dissociation and Flail chest

Slipped Capital Femoral Epiphysis (SCFE)

- TEAEs with a PT: Epiphyseal disorder, Epiphyseal injury

Avascular necrosis and osteonecrosis

- TEAEs with a PT: Osteonecrosis, Osteonecrosis of jaw, Osteonecrosis of external auditory canal, Necrosis ischaemic

Events of interest will be summarized as follows:

- Incidence and exposure-adjusted event rates of ISR events by PT
- Incidence and exposure-adjusted event rates of hypotension by PT
- Incidence and exposure-adjusted event rates of heart rate change events by PT
- Incidence and exposure-adjusted event rates of hypersensitivity (SMQ)
- Profile of ISRs
- Profile of hypotension
- Profile of heart rate change events

Profile summaries include: highest CTCAE grade, number of events per subject, time from first dose to first event onset, duration of events (days), action taken with study treatment, outcome of events.

Listings:

In addition to the above tables the following EOI listings are also provided:

- TEAEs of injection site reaction
- TEAEs of hypotension
- TEAEs of documented symptomatic hypotension
- TEAEs of heart rate change events
- TEAEs of hypersensitivity (SMQ)
- TEAEs of algorithmic anaphylaxis (SMQ) with sponsor-defined time restrictions
- TEAEs of fractures
- TEAEs of SCFE
- TEAEs of avascular necrosis and osteonecrosis

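### The heart rate change event of interest is searched with nine condition terms and no measured-value term, unlike the hypotension list beside it, so an event coded as a heart rate reading would be left out of the grouped outputs

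*SAP*

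**What the plan says.** SAP Version 2, Section 15.1.2 (Events of Interest) defines each event of interest by a coding rule. For heart rate change the rule is an enumerated list. It opens with "TEAEs with a PT: Atrial tachycardia, Postural orthostatic tachycardia syndrome, Rebound tachycardia, Sinus tachycardia, Supraventricular tachycardia" and closes with "Supraventricular tachycardia, Tachycardia, Tachycardia paroxysmal, Ventricular tachycardia, Bradycardia".

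The hypotension rule, immediately above it, is also an enumerated list. It combines "Blood pressure ambulatory decreased, Blood pressure decreased, Blood pressure diastolic decreased, Blood pressure orthostatic decreased, Blood pressure systolic decreased, Blood pressure systolic inspiratory decreased" with "Diastolic hypotension, Hypotension, Orthostatic hypotension".

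Three outputs rest on the heart rate list: the table "Incidence and exposure-adjusted event rates of heart rate change events by PT", the summary "Profile of heart rate change events" and the listing "TEAEs of heart rate change events".

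Version 1.1, bound in the same file, has the same heart rate list. Nothing in either version extends it. The review of adverse events before database lock in Section 15.1.1 provides for updating the achondroplasia-related list only.

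**The concern.** The hypotension list shows that, for blood pressure, the plan expects a reported reading and a reported condition to fall under different preferred terms, and it searches for both. The heart rate list searches for conditions only, although the category is named for change in general and Section 15.5 tabulates ECG heart rate in both directions. If a site reports a high or low heart rate as a reading and it is coded as one, the event falls outside the group.

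What is at stake is the completeness of one event-of-interest group chosen by the sponsor, in a trial where safety is a primary objective (Section 4.1). The profile of time to onset, duration, action taken and outcome is produced only for events inside such a group, so an event outside the list gets no profile.

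**Working it through.** The SAP states no figure on this point, so the check is a count of terms followed by a comparison of sections.

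**1. Terms in the heart rate list (Section 15.1.2).** The opening quote holds five terms. The closing quote holds five, and the two share one (supraventricular tachycardia). Total: 5 + 5 − 1 = 9. By type: 8 tachycardia + 1 bradycardia + 0 measured-value = 9.

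**2. Terms in the hypotension list (same section).** 6 measured-value (a form of blood pressure decreased) + 3 condition (a form of hypotension) = 9.

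**3. Where an event coded as a heart rate reading would and would not appear.**

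| Output | SAP section | Included? |
|---|---|---|
| Heart rate change incidence and exposure-adjusted rate | 15.1.2 | No |
| Heart rate change profile | 15.1.2 | No |
| Heart rate change listing | 15.1.2 | No |
| All treatment-emergent events by preferred term, with rates | 15.1.1 | Yes |
| Listing of all treatment-emergent events | 15.1.1 | Yes |

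**4. Whether the measured data fill the gap.**
- Section 15.3 summarizes pre-dose heart rate and its change from baseline, and plots mean pre-dose and post-dose values. Its threshold and shift tables (a 20% diastolic fall, diastolic cut-offs of 40 and 30 mmHg, an age-based systolic cut-off) are for blood pressure only.
- Section 15.5 reports the percentage of subjects with a post-dose ECG heart rate rise of more than 25% to above 100 beats/min, or a fall of more than 25% to below 50 beats/min. This does not depend on adverse event reporting, but it covers ECG visits only. Days 2 and 3 and Week 3 are vital-sign visits in Section 15.3 and are not ECG visits in Section 15.5.

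These outputs cover part of the ground. None of them is a profile of reported events.

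**5. Size.** If N heart rate events are reported and a fraction f is coded as readings, the group captures N × (1 − f). The SAP gives neither N nor f, and f = 0 is possible. As a scale only: at the minimum randomized numbers in Section 4.2 (27, 17 and 17), 1:1 allocation gives about 13 to 14 subjects per arm in Cohort 1 and 8 to 9 in Cohorts 2 and 3. One subject whose only heart rate event was coded as a reading would then change a randomized arm's group incidence by 1/14 = 7.1 to 1/13 = 7.7 percentage points in Cohort 1, and by 1/9 = 11.1 to 1/8 = 12.5 points in Cohorts 2 and 3. Whether any such subject exists is not known from the SAP.

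**The case against.** The strongest reply is that the breadth of a search is the sponsor's choice and that this list contradicts nothing. Section 15.1.2 builds its events of interest in several ways (a high-level term, standardized queries, a text string, term lists) and sets no common standard. The SAP does not reproduce MedDRA, so it does not show which heart rate reading terms exist in Version 24.1. It also does not say whether sites report isolated readings or diagnoses; that rule may sit in the protocol. Frequent measurement after dosing does not show that readings become adverse events. Any event left out of the group is still reported elsewhere.

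All of this stands as a limit on the claim. It does not explain why readings are searched for blood pressure and not for heart rate in adjacent lists, and no other section says the omission is intended.

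Three stronger readings are tempting, and the SAP does not support them:
- **A definite undercount of a stated size.** Any particular fraction would be a guess; the text supports only that events could be missed.
- **That slowing is captured worse than quickening, because one term stands against eight.** A count of terms is not a share of events. The tachycardia terms are largely subtypes, and the general bradycardia term is in the list.
- **That such events disappear from the report.** Section 15.1.1 keeps them in the general tables and in the full listing.

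**Conclusion.** The point holds as a minor gap in ascertainment. The heart rate list has no measured-value term, the neighbouring hypotension list has six, and no rule extends the heart rate list before lock. A heart rate event coded as a reading would be left out of the grouped incidence, rate, profile and listing, and kept in the general adverse event outputs. The size of any undercount cannot be determined from the SAP and may be zero.

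The conclusion rests on one assumption: that MedDRA 24.1 keeps heart rate readings apart from heart rate conditions, as the SAP's own hypotension list shows it does for blood pressure. This has to be confirmed in the dictionary. No efficacy analysis and no overall adverse event total is affected.

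**What to change.** Before database lock, while the study is still blinded (Section 4.6.1), check MedDRA 24.1 and add to the heart rate change list the preferred terms for increased and decreased heart rate readings, and a sinus counterpart for bradycardia if the dictionary has one. The list would then be built like the hypotension list. Record the change in Section 24, which already records a revision of another definition in Section 15.1.2. If lock has passed, keep the list as it is and run the wider search as a supplementary analysis labelled as such. If the omission was deliberate, one sentence of explanation in Section 15.1.2 would settle the matter.

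The cost is a longer term list in the SAP and the programming specification, with no new data. The downside is that some non-specific readings enter the event count. They stay visible, because the table is broken down by preferred term.
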